## **Randomized controlled study of PR-ESSENCE - a problem-solving model for youth with challenging behavior in SiS youth homes.**

### **Background**

The "Collaborative Problem Solving" (CPS) model was developed by psychologist Ross Greene, Harvard University, and is presently referred to as "Collaborative and Proactive Solutions". The method is based on the theory that challenging behavior is due to lagging skills, especially in the areas of cognitive flexibility, frustration tolerance and problem-solving ability. With the model, adults and youth collaborate to analyze triggers for problematic behaviors, suggest possible problem solutions and strategies which may benefit both parties, and practice them systematically in everyday life.

The CPS model has been evaluated in US studies, and our research group performed a pilot study in Sweden for children with ADHD and Oppositional Defiant Disorder (ODD). Based on experiences, our team has since adapted the CPS-method to children with complex neurodevelopmental disorders. We use the term ESSENCE (Early Symptomatic Syndromes Eliciting Neuropsychiatric Examinations), an umbrella term for neurodevelopmental disorders in children, and we call our model PR-ESSENCE (Problem Resolution for ESSENCE).

#### *The Gillberg Neuropsychiatry Centre (GNC) PR-ESSENCE trial 2014-2019*

We recently conducted a randomized controlled trial (RCT) with 108 children and adolescents aged 5-18 years, with ESSENCE and challenging behaviors (submitted). The active group received PR-ESSENCE training for 10 weeks. The control group received "treatment as usual (TAU)" for 10 weeks (that is information, support and individualized treatment according to standard treatment guidelines), followed by 10 weeks of PR-ESSENCE-training. The 10-week PR-ESSENCE treatment period included a visit once a week when parents and children met the therapists to learn the method and to collaborate in finding problem solution strategies, which the families then practiced at home between visits. Primary outcome was Clinical Global Impression-Improvement (CGI-I) ratings by independent blinded assessors, based on all available information. Outcome data were collected at baseline, post-treatment/control period, after 6 months and 1 year. Clinical response was defined as being much or very much improved on the CGI-I. At post-treatment 51.4% in the active group were responders, compared to 5.6% in the control group. After 1 year 63% of all were responders, which suggests a long-term consolidated learning and change in relations and behavior patterns.

### **The PR-ESSENCE SiS youth home trial 2021-2024**

#### *Design*

Inspired by the results of the GNC trial described above we plan to test the method in an RCT with similar design for youth with challenging behaviors in SiS Youth Homes. During three years 60-70 youth will be included in the trial. They will be randomized 1:1 to active group or control group. The active group will receive PR-ESSENCE training for 10 weeks. The control group will receive "treatment as usual (TAU)" for 10 weeks, followed by 10 weeks of PR-ESSENCE treatment.

#### *Research questions*

Can the PR-ESSENCE-method reduce problem behaviors, solve problematic situations, and improve psychological well-being and self-image for youth resident in SiS Youth Homes?

#### *Inclusion criteria*

1. Youth with challenging behavior who are placed (at least 3 months) at SiS Youth Home for boys (Nereby), and girls (Björkbacken).
2. Age according to SiS framework (12-17 years).
3. Intellectual function in the normal range, according to WISC-test and clinical judgment.

4. Broset Violence Checklist (BVC) - ratings, at least 5 points of problem behaviors per week (points per week are calculated from the daily ratings during 2 weeks before the screening period, and the score of the week with most points is used for inclusion).
5. YLS/CMI domain 7 (behavior problems) score indicates medium to high risk
6. Medication allowed if stable at least one month before baseline and during the trial.

*Exclusion criteria*

1. Intellectual disability, bipolar disorder, psychosis, substance use, or other unstable psychiatric or medical condition which could entail risk or limit participation in the trial.

**Outcome measures**

All outcome data will be collected at baseline, at post-treatment/control period follow-up, and as long-term follow-up before the youth leaves the SiS home (this time point may vary several months).

*Ratings by independent blinded assessor*

Clinical Global Impression-Improvement (CGI-I): Scale for rating of global improvement or worsening of problems/symptoms (score range 1-7; 1 very much improved, 7 very much worse) (Guy 1976).

Clinical Global Impression-Severity (CGI-S): Scale for rating of global problem/symptom severity (score range 1-7; 1 no problems, 7 extreme problems) (Guy 1976).

*Ratings by contact persons*

Broset Violence Checklist (BVC) - ratings of daily problem behaviors

SNAP – IV – Swanson, Nolan and Pelham scale. Rating scale for ADHD- and oppositional symptoms (Swanson 1992).

ECBI - Eyberg Child Behavior Inventory – rating scale for challenging behaviors (Eyberg & Pincus 1999).

RPQ - Relationship Problems Questionnaire – rating scale for relationship problems (Minnis et al 2002)

*Youth self-ratings*

BYI - Beck Youth Inventories - interview about symptoms of depression, anxiety, irritability, challenging behavior, self-image (Beck et al 2005).

**Screening (at the youth home during 2 weeks before baseline)**

*Informed consent* from youth and parents/caregiver (collected by Coordinator)

*Psychologist assessments:*

- YLS/CMI (standard assessment for all youth at arrival to SiS home).
- DSM-5-diagnostic screening for psychiatric problems
- WISC-V test of intellectual level

*Youth self-rating (with psychologist):*

- BYI for assessment of psychological well-being and self-image

*A-TAC-interview:* Parents/caregivers interviewed by therapist to screen for neuropsychiatric problems

*BVC-ratings* of problem behaviors, made daily during 2 weeks by contact persons at the youth home (ward and school). Results are used as inclusion criterium

**Screening visit at GNC – or videolink:**

Coordinator and contact persons from the youth home together with the GNC *blinded assessor* assess the screening results and inclusion/exclusion criteria.

*Randomisation*

Computer-generated unstratified block-randomisation (blocks of 4-8 youth) 1:1 to treatment or control, is performed by independent project leader

*Primary outcome*

- CGI-I rated by blinded assessor

*Secondary outcomes* (change from baseline measured with the following instruments):

- CGI-S rated by blinded assessor
- Ratings by the youth's contact person:
  - BVC (number/intensity of problem situations)
  - SNAP-IV (ADHD and oppositional symptoms)
  - ECBI (challenging behaviors)
  - RPQ (relationship problems)
- BYI (youth self-ratings)
- Therapist-ratings with the Problem Rating Scale (measures how many problem situations could be wholly or partially solved).

*Active group:* Contact person and youth learn and practice the method at weekly visits with therapist for 10 weeks, and practice problem solution strategies in everyday life between visits. Therapists will be given supervision and support once monthly from therapists in our GNC research team.

*Control group:* Receives "treatment as usual" during the 10-week control period, and thereafter 10 weeks of PR-ESSENCE-training.

*Continuous evaluations during the trial*

- BVC-ratings of problem behaviors will be made daily during the whole trial, by contact persons at the youth home (ward and school). Weekly results will be collected.
- With the Problem Rating Scale, the therapists will at each visit rate the number of problem situations which have been wholly or partially solved.

*Statistical plan*

Sample size calculation indicates that with power 0.80 and significance level of .05, a sample of 52 participants would be required to detect an effect size (Cohen's *d*) of 0.7, which may be considered as a clinically meaningful effect. Previous research has shown larger effect sizes on the primary outcome measure CGI-I. Primary and secondary efficacy analyses will be performed on all randomized subjects (Intention-to-Treat (ITT) population) with baseline values carried forward to endpoint for dropouts, on the Full Analysis Set (FA set) defined as all randomized subjects with any baseline and any end of treatment measurements, and on the Per Protocol population (subjects who completely followed the protocol). Analyses of covariance, covarying for baseline values, will be used to compare posttreatment assessment scores in the PR-ESSENCE versus control groups. For comparison between the groups Mantel-Haenszel chi-square test will be used for ordered categorical variables, Fisher's exact test for dichotomous variables and Pearson chi-square for non-ordered categorical variables. For dichotomous variables the risk difference with 95% CI and the risk ratio with 95% CI will be presented. Effect Sizes (ES) will be calculated as the difference in mean scores between PR-ESSENCE group and controls, divided by the pooled standard deviation. The distribution of continuous and interval scaled variables will be reported as mean, SD, median, minimum and maximum and distribution of categorical variables as numbers and percentages.

*Dissemination*

Our research team will collect and analyze all data, write research reports, publish the study results on group level in international journals, and present results on national and international conferences. Education and supervision on the method can be provided to other SiS youth homes on demand.

*Future perspectives*

The GNC trial provided new knowledge about solutions for behavior problems and conflict management. We hope that PR-ESSENCE training in SiS Youth Homes can give long-term improvements in self-regulation abilities and conflict solutions, and thereby prevent challenging, disruptive and antisocial behaviors. If lasting improvements in problem-solving abilities and

interaction could reduce violence, drug use and criminality, this would give large psychological and economic gains for families and society.

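### Contact persons trained in PR-ESSENCE with the youth also rate SNAP-IV, ECBI, RPQ and at least part of BVC, so arm differences on these secondary outcomes can mix youth change with rater change

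*Combined protocol and SAP*

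**What the plan says.** All references are to the combined protocol and SAP.

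- **Who is trained.** The Active group paragraph (under Screening visit at GNC – or videolink) states: "Contact person and youth learn and practice the method at weekly visits with therapist for 10 weeks". The pair also "practice problem solution strategies in everyday life between visits".
- **Who rates.** The Secondary outcomes list puts BVC, SNAP-IV, ECBI and RPQ under "Ratings by the youth's contact person". Outcome measures assigns the same four to contact persons, beginning with "Broset Violence Checklist (BVC) - ratings of daily problem behaviors".
- **BVC has more than one setting.** At screening it is "made daily during 2 weeks by contact persons at the youth home (ward and school"). Under Continuous evaluations, "BVC-ratings of problem behaviors will be made daily during the whole trial, by contact persons at the youth home (ward and school").
- **Control arm.** Control youth have usual treatment for the 10 weeks of the comparison and start PR-ESSENCE only afterwards (Design; Control group).
- **What is blinded.** The primary outcome is "CGI-I rated by blinded assessor". CGI-S is also rated by the blinded assessor. BYI is a self-rating, and the Problem Rating Scale is completed by therapists.
- **Analysis.** The Statistical plan compares post-treatment scores by analysis of covariance on baseline. It has no provision for rater effects.

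The plan does not say which contact persons attend the visits, does not require training and rating to be done by different staff, and does not place the baseline SNAP-IV, ECBI and RPQ before or after randomisation.

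**The concern.** By week 10 the raters in the two arms are no longer comparable. The active-arm contact person knows the allocation, has spent ten weeks working on the youth's problems, and has been taught a particular account of them: the Background explains challenging behavior as a matter of lagging skills. Such a rater may score unchanged behavior differently. On RPQ the rater may also be one side of the relationship being treated.

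At stake is the reading of the scales that speak most directly to the research question about reducing problem behavior. The Statistical plan gives them the same efficacy analysis as the other outcomes, with no caveat, so a significant result on ECBI or BVC could be reported as change in the youth when part or all of it is change in the rater.

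**Working it through.** **Step 1. Does the overlap differ by arm?** Set the paragraphs side by side.

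| | Active arm, weeks 0-10 | Control arm, weeks 0-10 |
|---|---|---|
| Contact person trained with this youth | yes, weekly | no, only afterwards |
| SNAP-IV, ECBI, RPQ rater | contact person | contact person |
| BVC raters | contact persons, ward and school | contact persons, ward and school |
| CGI-I, CGI-S rater | blinded assessor | blinded assessor |

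The overlap of trainee and rater exists in one arm only at the time of the comparison, so it does not cancel between arms. For BVC the overlap may be partial: two settings rate, and the plan does not say whether staff from one or both attend.

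**Step 2. Does the planned analysis remove it?** Write the post-treatment score as baseline effect + youth effect + b × (active arm), where b is the shift in the trained rater's scoring. The covariate is measured before b arises, and b coincides with the arm indicator. The adjusted arm difference therefore estimates the youth effect plus b.

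**Step 3. How much could it matter?** No figure in the plan is disputed, so there is none to reproduce. The illustration uses:

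- n per arm: 60-70 youth randomised 1:1 (Design), so 60/2 = 30 to 70/2 = 35.
- Significance level .05 (Statistical plan). Sidedness is not stated; two-sided is assumed.
- True youth effect: zero (assumed).
- Rater shift b: 0.2, 0.3 or 0.5 SD (assumed; the documents give none).

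With an unadjusted two-sample t-test, the statistic follows a non-central t distribution with 2n − 2 degrees of freedom and non-centrality b × √(n/2). For example, b = 0.3 and n = 30 give 0.3 × √15 = 1.16.

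| b (SD) | Non-centrality, n = 30 | P(p < .05), n = 30 | Non-centrality, n = 35 | P(p < .05), n = 35 |
|---|---|---|---|---|
| 0 | 0 | 5% | 0 | 5% |
| 0.2 | 0.77 | 12% | 0.84 | 13% |
| 0.3 | 1.16 | 21% | 1.25 | 24% |
| 0.5 | 1.94 | 48% | 2.09 | 54% |

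The planned covariance analysis would not lower these rates. It reduces residual variance but leaves b in place. At an assumed baseline correlation of 0.5, b is divided by √(1 − 0.25) = 0.866, and the three rates become 14-16%, 26-30% and 59-66%.

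**Step 4. Baseline order.** The Screening section lists BVC and BYI but not SNAP-IV, ECBI or RPQ. Outcome measures says all outcomes are collected at baseline, and screening precedes baseline. The Randomisation paragraph follows the screening-visit paragraph. Nothing fixes whether the three remaining forms come before or after allocation, so the order is open.

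**The case against.** The strongest reply is that only secondary outcomes are affected: CGI-I and CGI-S already have a blinded assessor. An intervention delivered through a caregiver also makes unblinded caregiver ratings hard to avoid. On RPQ, a changed view by the contact person may partly be real change in the relationship, which the method aims at. All of this stands, and it limits the importance of the point. It does not excuse the missing caveat, nor the failure to use the BVC ratings that may come from staff outside the visits.

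It can also be said that the error rates rest wholly on assumed shifts. That is correct. Training could equally make a rater more alert to problems, which would work against PR-ESSENCE.

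A reader might draw four stronger conclusions that the documents do not support:

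- **That these outcomes are shown to be biased in favour of PR-ESSENCE.** The text establishes a mechanism, not its size or sign.
- **That every BVC rating comes from a trained person.** Ward and school both rate, and attendance is unspecified.
- **That baseline SNAP-IV, ECBI and RPQ are completed after allocation.** The order of headings does not establish this; the sequence is merely unstated.
- **That the primary outcome is compromised because contact persons inform it.** The earlier GNC trial based CGI-I on all available information, but this plan does not say what its assessor uses.

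Finally, a colleague who does not attend the visits is not blinded, and control youth have no visits during the comparison. A rule based on actual attendance would therefore be undefined in one arm. The fix has to allow for both.

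**Conclusion.** The point holds as a risk of bias in secondary outcomes. For SNAP-IV, ECBI, RPQ and at least part of BVC, the active-arm rater is a participant in the treatment, the control-arm rater is not yet one, and adjustment for baseline cannot separate rater change from youth change. The false-positive rates of 12-13%, 21-24% and 48-54% per scale are conditional on assumed shifts of 0.2, 0.3 and 0.5 SD, no true effect and 30-35 per arm. They show that a modest shift would matter, not that one exists. Baseline timing for three of the scales needs clarification and is not a demonstrated error. The change is worth making because it is cheap and largely reuses data already being collected; the blinded CGI-I keeps it from being a central flaw.

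**What to change.** 1. **BVC.** Before randomisation, name for every youth in both arms the contact person or persons who will attend PR-ESSENCE visits (control youth attend later). Record the rater and the setting, ward or school, on each BVC form. Pre-specify a between-arm BVC analysis within setting, with the same baseline adjustment, that uses only ratings by staff not named as attending, and report it beside the all-rater result. Where all of a youth's BVC raters are named as attending, say so and report how many youths this affects. Describe the non-attending ratings as independent of the training, not as blinded.
2. **Baseline forms.** State that SNAP-IV, ECBI and RPQ are completed before randomisation. BVC and BYI are already collected at screening.
3. **Interpretation.** State that SNAP-IV, ECBI, RPQ and BVC ratings by attending staff are unblinded ratings by treatment participants and are supportive only, with efficacy conclusions resting on the blinded CGI-I and CGI-S.

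**Cost.** A short list made before randomisation, two fields on the BVC form, a fixed order for three baseline forms, one added analysis and a few sentences. The non-attending BVC analysis will have fewer rated days, and possibly fewer youths, so it will be less precise. If staff from both settings attend for most youths, it may be too sparse to be useful, and the report should say so.

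### The stated 52 participants does not give 80% power for d = 0.7 at two-sided .05; an unadjusted comparison needs 66-68, and the planned 60-70 gives 0.76-0.82 before dropout

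*Combined protocol and SAP*

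**What the plan says.** The sample-size statement under *Statistical plan* reads "with power 0.80 and significance level of .05, a sample of 52 participants would be required to detect an effect size". The target is d = 0.7, which the plan regards as clinically meaningful. It adds: "Previous research has shown larger effect sizes on the primary outcome measure CGI-I". It gives no sidedness, test, baseline correlation or dropout allowance.

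Under *Design*, allocation is 1:1 and "During three years 60-70 youth will be included in the trial".

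The primary outcome is CGI-I, described under *Outcome measures* as a "Scale for rating of global improvement or worsening of problems/symptoms", scored 1 to 7.

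The analyses named under *Statistical plan* are ANCOVA on baseline for scores, then "Mantel-Haenszel chi-square test will be used for ordered categorical variables", with Fisher's exact and Pearson chi-square tests for other categorical variables. Also: "For dichotomous variables the risk difference with 95% CI and the risk ratio with 95% CI will be presented". The intention-to-treat analysis is run "with baseline values carried forward to endpoint for dropouts".

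**The concern.** A two-group comparison at d = 0.7 with 80% power usually needs more than 52 participants when the test is two-sided. Nothing in the plan declares a one-sided test, and the named tests and 95% intervals are two-sided by convention. A reader who takes the significance level as two-sided cannot reproduce the figure.

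Against a requirement of 52, enrolling 60-70 looks like a reserve of 8 to 18 youth for dropout. If the true requirement is 66-68, then 60 is short by 6 to 8 and 70 leaves only 2 to 4 to spare. If sidedness stays open until results are known, it could also be chosen after the fact.

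**Working it through.** **Inputs.** From *Statistical plan*: d = 0.7, power 0.80, level .05, N = 52. From *Design*: 1:1 allocation, 60-70 enrolled. Sidedness is not stated, so both versions are computed.

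**Normal approximation, per group:** n = 2(z_α + z_β)² / d².

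- One-sided .05: 2(1.645 + 0.842)² / 0.49 = 25.23, so 26 per group and **52** in total. This reproduces the plan's figure.
- Two-sided .05: 2(1.960 + 0.842)² / 0.49 = 32.04, so 33 per group and **66** in total.

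**Two-sample t-test (noncentral t), per group for 80% power:**

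| d | Level | n per group | Total |
|---|---|---|---|
| 0.7 | one-sided .05 | 25.94 | 52 |
| 0.7 | two-sided .05 | 33.02 | 68 |
| 0.8 | two-sided .05 | 25.52 | 52 |

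So 52 also fits d = 0.8 at two-sided .05 (power 0.807).

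**Two-sided power for d = 0.7.** The noncentrality is 0.7·√(N/4) on N − 2 degrees of freedom; at N = 52 it is 0.7·√13 = 2.52 against a critical value of 2.01. The last column is a simulated Mantel-Haenszel chi-square (1 df) on a 7-level score scaled to d = 0.7, with 60,000 runs per N.

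| N | Noncentrality | t-test power | Mantel-Haenszel power |
|---|---|---|---|
| 52 | 2.52 | 0.697 | 0.695 |
| 60 | 2.71 | 0.760 | 0.758 |
| 66 | 2.84 | 0.7997 | 0.797 |
| 68 | 2.89 | 0.812 | 0.807 |
| 70 | 2.93 | 0.823 | 0.817 |

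The d detectable with 80% power, two-sided, is 0.79 at 52, 0.74 at 60 and 0.68 at 70.

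**ANCOVA.** Adjusting for a baseline with correlation r raises the effective effect to 0.7/√(1 − r²), on N − 3 degrees of freedom. Two-sided power reaches 0.80 at r = 0.469 for N = 52 and at r = 0.308 for N = 60.

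**Dropout.** The plan states no rate, so 5% and 10%, equal in both groups, are assumptions, as is a control mean at no change. Under baseline carried forward, the effective d is 0.7·√((1 − p)/(1 + 0.245p)) if every dropout is scored as no change, or 0.7(1 − p) if the SD is unaffected.

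| Dropout p | Effective d | Power at 60 | Power at 70 |
|---|---|---|---|
| 5% | 0.678 or 0.665 | 0.733 or 0.717 | 0.799 or 0.783 |
| 10% | 0.656 or 0.630 | 0.705 or 0.670 | 0.772 or 0.738 |

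**The case against.** The strongest reply is that 52 is not a slip of arithmetic: it is exactly the one-sided .05 answer, and the plan never says two-sided. That is true, and two-sidedness here is inferred from convention; the 95% intervals are promised only for dichotomous variables. But a one-sided primary test has to be declared in advance, and none is. The sentence needs repair either way.

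Second, 66-68 is the requirement for an unadjusted test, whereas the plan names ANCOVA for scores. A baseline correlation of about 0.31 would bring 60 participants to 80%, and about 0.47 would do so for 52. This may well help the secondary scales. For CGI-I it cannot be assumed: the scale rates improvement, so it has no baseline value of its own, and no correlation is stated.

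Third, the trial will enrol 60-70, not 52, and larger effects are expected. This limits the damage. At d = 0.8, 60-70 gives two-sided power of 0.86 to 0.91. If the earlier trial's response rates (51.4% against 5.6%) recurred and response were the analysed form, two-sided Fisher's exact power would be 0.96 at 52 and 0.98 at 60. The plan, however, attached 80% to d = 0.7. That statement is not made correct by a more favourable scenario, and the earlier trial worked with parents at home rather than with contact persons in youth homes.

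Finally, the dropout figures rest on assumed rates. They illustrate the direction of the loss; the conclusion does not depend on them.

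**Conclusion.** The concern holds. Read as two-sided, which is how the named analyses are ordinarily run, the sample-size statement is wrong: 52 gives power of about 0.70 for d = 0.7, and an unadjusted comparison needs 66 (normal approximation) or 68 (t-test). Planned enrolment reaches 80% only at its upper end and only without loss. At 60 the deficit is four percentage points (0.76 against 0.80).

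This rests on two assumptions: a two-sided test, and no useful baseline adjustment for CGI-I. The practical consequence is moderate. It does not undermine the design, and power would be ample if effects approached those of the earlier trial.

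**What to change.** State the sidedness of the .05 level and name the test behind the calculation; two-sided fits the analyses listed. Then take one of these routes:

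- Correct 52 to 68 for d = 0.7 (66 gives 79.97% by the t-test).
- Keep 60-70 and restate its two-sided power for d = 0.7 as 0.76 at 60 and 0.82 at 70, before dropout.
- If 52 came from d = 0.8 or from an ANCOVA, state that effect size, or the assumed baseline correlation (about 0.47 at 52) and which outcome it applies to.

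If a one-sided test was intended, declare and justify it before results are seen. The cost is one or two sentences and a less favourable stated figure. The recruitment target, design and analyses need not change.

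### Home, which is the same variable as sex, is known before the unstratified randomisation but enters no planned analysis; pre-specifying it is a cheap, low-priority improvement.

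*Combined protocol and SAP*

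**What the plan says.** - **Two homes, split by sex.** The first inclusion criterion requires placement "at SiS Youth Home for boys (Nereby), and girls" (the second home is named there). Home therefore determines sex, and sex determines home.
- **Known in advance.** The screening section is headed "Screening (at the youth home during 2 weeks before baseline", so each youth's home is on record before allocation.
- **Not used in allocation.** The randomisation paragraph specifies "Computer-generated unstratified block-randomisation (blocks of 4-8 youth) 1:1 to treatment or control".
- **Not used in analysis.** The Statistical plan says "Analyses of covariance, covarying for baseline values, will be used to compare posttreatment assessment scores in the PR-ESSENCE versus control groups". For other variable types, "Mantel-Haenszel chi-square test will be used for ordered categorical variables", with Fisher's exact test for dichotomous and Pearson's chi-square for unordered variables. No home or sex term, stratum or subgroup is named.
- **Size.** The Design section plans 60-70 youth. The Statistical plan derives 52 from d=0.7, power 0.80 and significance level .05.

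**The concern.** The two homes differ in the sex of their residents, and presumably in staff and daily routine, so outcomes may differ between them. Neither the design nor the analysis deals with this. In a trial of 60-70 youth, unstratified blocks can leave the arms with visibly different shares of boys and girls. If home is prognostic, the unadjusted comparison in that trial is shifted by roughly the home effect times the gap in share, and the variance due to home stays in the error term. If such a gap appears and the plan is silent, adding sex afterwards looks data-driven, while leaving it out invites challenge. A choice made before outcome data are seen avoids both.

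**Working it through.** **Inputs from the documents:** d=0.7, alpha 0.05, 1:1 allocation, unstratified blocks of 4-8, N=60-70, two homes.

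**Assumptions, because the documents give no figure:** two-sided testing; SD within arm of 1; each youth equally likely from either home; block sizes 4, 6 or 8; home effects of 0, 0.3, 0.5 and 0.8 SD.

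**1. The plan's own figure.** For a two-sample t test with 26 per arm, the noncentrality is 0.7 × √(52/4) = 2.524. Power is 0.801 one-sided and 0.697 two-sided. The plan's 52 therefore reproduces as a one-sided test. It also reproduces two-sided if the baseline covariate is assumed to correlate about 0.47-0.50 with outcome. The plan states neither. The two-sided figures below are the more cautious choice.

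**2. How often the arms differ in home share.** In simulated allocations, a gap of 20 points or more occurs in about 15% of trials of 60 and 11-12% of trials of 70. Across assumed home mixes from 50:50 to 67:33, whether random or fixed, the ranges are 12-18% and 9-14%.

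**3. What such a gap does.** The mean gap in those trials at N=60 is about 0.24. The unadjusted estimate shifts by about 0.24 × 0.5 = 0.12 SD or 0.24 × 0.8 = 0.19 SD (0.20 by simulation). Within those trials, unadjusted type I error is about 0.07 and 0.10, against about 0.05 adjusted. Over all trials both tests lie between 0.047 and 0.054.

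**4. Average power with and without home, no baseline covariate.**
- Unadjusted noncentrality: 0.7 × √(N/4), with N−2 df. This is 2.711 at N=60 and 2.928 at N=70.
- Adjusted: divide by √[(1−R²)(1+1/(N−4))], with N−3 df. With equal homes, R² = (home effect)²/4.
- Example, N=60 and 0.5 SD: R² = 0.0625, noncentrality 2.711/√(0.9375 × 1.0179) = 2.775, power 0.779.

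| N | Unadjusted | Adjusted, 0 SD | 0.3 SD | 0.5 SD | 0.8 SD |
|---|---|---|---|---|---|
| 60 | 0.760 | 0.752 | 0.762 | 0.779 | 0.822 |
| 70 | 0.823 | 0.817 | 0.826 | 0.841 | 0.878 |

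Break-even is R² = 0.0181 at N=60 and 0.0154 at N=70. The home effect there is 2√R² = 0.27 and 0.25 SD.

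**5. Cost on the same footing as step 3.** For a given allocation, the noncentrality is multiplied by √(1−r²), where r is the correlation between arm and home. With no home effect, the mean loss over all allocations is 0.8 points (N=60) and 0.6 (N=70). In allocations with a gap of 20 points or more it is about 2.8 and 2.4-2.5 points.

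**6. With a baseline covariate** (N=60, assumed correlation 0.5), power changes as follows when home is added:
- no home effect: 0.866 to 0.859;
- 0.5 SD at follow-up only: 0.856 to 0.878;
- 0.5 SD at both baseline and follow-up: 0.872 to 0.874.

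**7. Mantel-Haenszel test** (7-point scale, assumed control distribution 1/4.6/25/50/14.4/4/1%, latent d=0.7), unstratified to stratified:
- N=60: 0.702 to 0.695 (no home effect), 0.703 to 0.718 (0.5 SD), 0.708 to 0.764 (0.8 SD);
- N=70: 0.775 to 0.767, 0.775 to 0.789, 0.773 to 0.825.

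**The case against.** **The plan contains no error here.** The randomisation is openly unstratified and the analysis matches it. Adjusting for a factor not used in allocation is an option, not a requirement. This stands, and it limits the point to a suggestion.

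**The benefit rests on assumed home effects.** Nothing in the documents shows that home affects outcome. For scales with a baseline covariate, a stable home difference is already largely absorbed (step 6). If the earlier trial's response rates recurred (51.4% v 5.6%), Fisher power at N=60 is already about 0.98 and home hardly matters. This also stands.

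**Benefit and cost must be measured alike.** Setting a type I error in imbalanced trials against a cost averaged over all trials would flatter the fix. The cost in those same trials is about 2.5-3 points, not under one. Both figures are therefore given.

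**Stronger readings that the documents do not support:**
- A reader might infer from the 0.07 and 0.10 in step 3 that the planned tests are invalid. They are not: youth are randomised individually, and those figures apply only to a selected subset of allocations and to assumed home effects.
- A reader might extend the stratification to the dichotomous outcomes. Replacing Fisher's test with a stratified exact test raised power from 0.624 to 0.657 with no home effect at all (5.6% v an assumed 30%), while type I error also rose (0.006 to 0.011 at 5.6%). That reflects a less conservative test, not information from home.
- A reader might add that no baseline value is named for CGI-I. That is a missing detail unrelated to home, and forms no part of this point.

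**Conclusion.** The point holds as a low-priority, inexpensive improvement. Home/sex is known before allocation and is used nowhere in the analysis, and an imbalance of 20 points or more is a realistic event at this size. The expected loss if home is irrelevant is small. The gain turns positive once home explains about 1.5-1.8% of outcome variance, but the documents do not show whether it does. The firmer argument is pre-specification, which settles how an uneven sex mix will be handled before anyone knows which choice favours the treatment. The power figures rest on d=0.7, two-sided testing, equal recruitment from the homes and the assumed home effects. A home term cannot separate the effect of home from that of sex.

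**What to change.** Before outcome data are seen, add to the Statistical plan:
- home/sex as a fixed covariate in every ANCOVA, beside any baseline value;
- home/sex as the stratum in the Mantel-Haenszel test;
- the pooled within-arm SD kept as the effect-size denominator, so that the result stays comparable with the planned d=0.7;
- the term reported as home/sex, with a statement that the two cannot be separated.

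The unstratified randomisation can stay, as can Fisher's test, the risk difference and the risk ratio for dichotomous outcomes. The change needs one model term (1 df), one stratum variable already on record, and no extra data or participants. Its statistical price is the loss of power given in step 5 if home has no effect.
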